## 10.5.2 Criteria for Stopping Study Drug

At any time during the study, participants will stop of study drug if it is determined that they have experienced any of the following adverse events (refer to section 15.2 Table 3 for Adverse Event Grade Definitions):

- Any neuropsychiatric adverse event of Grade 3 severity
- Hallucinations of any severity (any Grade)
- Nausea of Grade 3 severity
- Vomiting of Grade 3 severity

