# 15.2 Adverse Event Grading

Adverse events will be graded according to the revised NCI Common Terminology Criteria for Adverse Events (NCI-CTCAE version 5.0).

If an AE is not listed in the NCI-CTCAE v.5.0, then the Physician will use the terms: mild, moderate, severe, life-threatening, or death to describe the maximum intensity of the AE. For purposes of consistency, these intensity grades are defined as follows:

Table 3.: Adverse Event Grade Definitions						
CDADE						

GRADE		
1	Mild	Mild; asymptomatic or mild symptoms; clinical or diagnostic observations only; intervention not indicated.
2	Moderate	Moderate; minimal, local or noninvasive intervention indicated; limiting age- appropriate instrumental ADL
3	Severe	Severe or medically significant but not immediately life-threatening; hospitalization or prolongation of hospitalization indicated; disabling; limiting self-care ADL
4	Life-threatening	Life-threatening consequences; urgent intervention indicated
5	Fatal	Death related to AE

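### Protocol 10.5.2 sets the neuropsychiatric stopping rule at Grade 3 without adding higher grades, so read literally an event first assessed at Grade 4 is not a mandatory stop (minor drafting error)

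*Protocol*

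**What the plan says.** Protocol section 10.5.2 is the mandatory, event-based stopping rule. It says that "participants will stop of study drug if it is determined that they have experienced any of the following adverse events" and then lists four items. Three name a single grade: "Any neuropsychiatric adverse event of Grade 3 severity", "Nausea of Grade 3 severity" and "Vomiting of Grade 3 severity". The fourth, hallucinations, applies at every grade. The list is not limited to events judged related to study drug.

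For the meaning of the grades, the rule tells the reader to "refer to section 15.2 Table 3 for Adverse Event Grade Definitions". In that table Grade 3 is "Severe or medically significant but not immediately life-threatening", and Grade 4 is its own level: "Life-threatening consequences; urgent intervention indicated". The text of section 15.2 makes NCI-CTCAE v5.0 the main grading scale and uses Table 3 for events that scale does not list.

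Section 10.5.1 contains the only other mandatory stop for toxicity. A patient already reduced to one capsule every 12 hours is discontinued for drug-related toxicity of Grade 2 or above.

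**The concern.** A stopping rule should become no less strict as the event becomes more severe. Table 3 defines Grade 3 so as to exclude immediately life-threatening events, so a Grade 4 event does not meet that definition. Taken at its word, the rule takes a patient off drug for a severe neuropsychiatric event but not for a life-threatening one of the same kind.

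The wording cannot be put down to a convention that a named grade means that grade and above. The hallucinations bullet in the same list covers all grades expressly, section 10.5.1 writes its Grade 2 thresholds as ranges, and SAP section 8.3 asks for summaries of events at Grade 3 or above. Where the documents intend a range, they say so.

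What is at stake is the clarity of a patient-safety instruction applied independently at about 15 sites. No estimate, endpoint or analysis depends on it.

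**Working it through.** No arithmetic applies. The check is to read the rule against every other provision that might require a stop.

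**Step 1: which events are in question.** Hallucinations are a stop at any grade and drop out. An event assessed at Grade 3 before worsening has already triggered the stop, because the rule turns on the patient having experienced such an event at any time in the study. What remains is a neuropsychiatric event other than a hallucination that is first assessed at Grade 4.

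**Step 2: what the mandatory provisions require for that event, read literally.**

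| Dose and causality | Assessed at Grade 3 | First assessed at Grade 4 |
|---|---|---|
| Full dose, related | Stop (10.5.2) | No mandatory stop |
| Full dose, unrelated | Stop (10.5.2) | No mandatory stop |
| One capsule every 12 hours, related | Stop (10.5.1 and 10.5.2) | Stop (10.5.1) |
| One capsule every 12 hours, unrelated | Stop (10.5.2) | No mandatory stop |

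The reversal is present at full dose whatever the causality, and at the reduced dose when the event is judged unrelated. It is absent at the reduced dose when the event is judged related.

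**Step 3: whether another provision closes the gap.**

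- The neuropsychiatric row of the table in 10.5.1 starts at Grade 2. It concerns opaganib-related toxicities likely to lead to discontinuation, asks for discussion with the sponsor, and sends the reader back to 10.5.2.
- Section 10.3 permits withdrawal for an adverse event on the investigator's judgment or in the patient's best interest. It does not require it, and its item on stopping criteria also refers back to 10.5.2.
- Section 14 requires immediate notification of life-threatening serious events. That is a reporting duty.
- The protocol's events of special interest (15.5.2) and the triggers for ad hoc DSMB meetings (15.5.4) concern oxygen requirement, inflammation and intubation, not neuropsychiatric events.

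None of these imposes a stop.

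**Step 4: which scale governs.** For neuropsychiatric terms not listed in NCI-CTCAE v5.0, Table 3 applies and has a Grade 4, so the gap is established. For listed terms, and for nausea and vomiting, section 15.2 puts NCI-CTCAE v5.0 first. Whether that scale has a Grade 4 for them cannot be read from the documents. If it has, the same gap applies; if it has not, there is none.

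**Step 5: effect of the amended wording.** With *Grade 3 or higher* in the bullet, every Grade 4 entry in the table becomes a stop under 10.5.2, and 10.5.1 needs no change.

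**The case against.** The strongest reply is that nobody would read the rule this way. The gap matters only if a site treats a stop for severe events as leave to continue through a life-threatening one. A Grade 4 event would also be a serious adverse event, with the sponsor and medical monitor told at once, and the investigator can stop treatment without waiting for a rule. The neuropsychiatric row of 10.5.1 does not repeat the dose-reduction option offered in the general row, which suggests that a stricter path was intended for these events. All of this stands and is why the point is minor. It does not make the rule correct, because none of these provisions is a mandatory stop.

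Three stronger readings are tempting, and the documents do not support them.

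- A reader might infer that the nausea and vomiting bullets are equally defective. That depends on a scale the documents do not reproduce.
- A reader might infer that the gap would often be met, since neuropsychiatric effects were reported in 14 of 21 patients in the solid-tumor study and 8 of 13 in the myeloma study (Protocol 6.4.1.1 and 6.4.1.2). Those counts are not given by grade, come from cancer patients at several doses including one above the trial dose, and in the myeloma study include hallucinations, already a stop. They say nothing about the rate of Grade 4 events.
- A reader might infer that the protocol intends treatment to continue through life-threatening events. Nothing in it suggests this; the evident intent is the opposite.

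**Conclusion.** The rule is wrong as written, and the error is a minor drafting one. The size is one bullet of four on the documents alone: the neuropsychiatric bullet, for events other than hallucinations first assessed at Grade 4, at full dose or at the reduced dose when judged unrelated. The nausea and vomiting bullets join it only on the assumption that the governing scale has a Grade 4 for them. The same assumption is needed for neuropsychiatric terms listed in NCI-CTCAE v5.0. The documents give no Grade 4 rate, so no expected number of affected patients can be stated. Practical risk is low.

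**What to change.** In Protocol 10.5.2, change the neuropsychiatric bullet to *Any neuropsychiatric adverse event of Grade 3 or higher*. Change the nausea and vomiting bullets to *Grade 3 or higher* as well, for consistency. Leave the hallucinations bullet and section 10.5.1 as they are.

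The edit is a few words. It is still a protocol modification, so under section 16.2.6 it needs IRB/EC approval before implementation, unless it is made to resolve an imminent safety issue. There is no cost in data collection or analysis.

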#### 11 PRIOR AND CONCOMITANT MEDICATIONS

#### 11.1.1 Prior Medications

Prior medications will include all recorded medications and supplements a patient was taking during the screening period that were stopped prior to administration of the study drug. These should be recorded in the eCRF.

#### 11.1.2 Allowed Medications

Necessary supportive measures for optimal medical care will be given throughout the study. Additional care may be administered as indicated by the treating physician and patient's medical need, and after discussion with the medical monitor.

#### 11.1.3 Concomitant medications

Concomitant medications will include all medications that started, or were continuing, during or after administration of the study drug. All concomitant medications and supportive therapy administered starting Day 1 and until the final off-study drug follow-up visit must be recorded on the appropriate eCRF page.

#### 11.1.4 Prohibited Medications

Medications that are sensitive CYP3A4, CYP1A2 CYP2C9, CYP2C19 or CYP2D6 substrates and have a narrow therapeutic index are prohibited. These should be decided in discussion with the Medical Monitor on a case-by-case basis.

Strong inducers or inhibitors of CYP2D6 and 3A4 are prohibited. These should be decided in discussion with the Medical Monitor on a case-by-case basis.

Warfarin, apixaban, argatroban and rivaroxaban are prohibited

#### 12 SCHEDULE OF EVENTS

#### 12.1.1 Procedures and Assessments

Please see "Schedule of Assessments" for a detailed study schedule (Section 4) presented in tabular form.

## 12.1.2 Screening (Day -3 to Day 1)

Prior to the initiation of study-specific screening assessments the Investigator or designee must provide the patient(s) a complete explanation of the purpose and evaluations (procedures and assessments) of the study. Subsequently, the patient, or legal representative, must sign and receive a copy of an Informed Consent Form and authorization of use and disclosure of protected health information (PHI) that was approved by the institutional review board (IRB). Once informed consent has been obtained, the eligibility of the patient will be determined, and Screening assessments will be performed. Screening may be performed prior to Baseline (Day -7 to -1) or on the same day as Baseline (Day 1)

- Signed informed consent
- Eligibility determination
- Complete medical history (including onset of COVID-19 symptoms)
- Concomitant medication assessment
- Baseline review of systems
- Physical examination
- Vital signs (temperature, blood pressure, pulse rate, respiratory rate and oxygen saturation by pulse oximeter)
- Weight if the patient is ambulatory
- Oxygen requirement (L/min)
- 12-lead electrocardiogram
- Chest Xray
- Nasopharyngeal or pharyngeal swab for SARS-CoV-2-PRC
- Serum chemistry
- CRP, D-Dimer, LDH, ferritin, cardiac troponin
- CBC with differential
- Urinalysis
- Serum pregnancy test (for women of childbearing potential) within 3 days prior to treatment

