#### **Study Duration**

Recruitment period is estimated at 3 months

The maximum duration of study participation will be up to 45 days (including up to 3 days screening; 2 weeks double-blind (DB) treatment phase and 4-weeks off-study drug follow-up)

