#### 9.2 Exclusion Criteria

- 1) Any co-morbidity that may add risk to the treatment in the judgement of the investigator.
- 2) Requiring intubation and mechanical ventilation
- 3) Patient having a do not intubate or do not resuscitate order
- 4) Oxygen saturation >95% on room air

- 5) Any preexisting respiratory condition that requires intermittent or continuous ambulatory oxygen prior to hospitalization
- 6) Patient is, in the investigator's clinical judgement, unlikely to survive >72 hours
- 7) Pregnant (positive serum test within 3 days prior to randomization) or nursing women
- 8) Unwillingness or inability to comply with procedures required in this protocol.
- 9) Corrected QT (QTc) interval on electrocardiogram (ECG) >470 ms for females or >450 ms for males, calculated using Friedericia's formula (QTcF)
- 10) AST (SGOT) or ALT (SGPT) > 5 x upper limit of normal (ULN)
- 11) Bilirubin >2x ULN (except where bilirubin increase is due to Gilbert's Syndrome)
- 12) Serum creatinine >2.0 X ULN
- 13) Absolute neutrophil count <1000 cells/mm^3
- 14) Platelet count <75,000/mm^3
- 15) Hemoglobin < 8.0 g/dL
- 16) Currently taking medications that are sensitive CYP3A4, CYP1A2, CYP2C9, CYP2C19 or CYP2D6 substrates and have a narrow therapeutic index. These should be decided in discussion with the Medical Monitor on a case-by-case basis.
- 17) Currently taking medications that are strong inducers or inhibitors of CYP2D6 and CYP3A4. These should be decided in discussion with the Medical Monitor on a case-by-case basis.
- 18) Currently taking warfarin, apixaban, argatroban or rivaroxaban
- 19) Current drug or alcohol abuse
- 20) Currently participating in a clinical study assessing pharmacological treatments, including antiviral studies

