#### 10 STUDY DESIGN

## **10.1 Overall Investigation Plan**

This is a phase 2a, proof of concept, multi-center randomized double-blind, parallel arm, placebo controlled study. The study is planned be performed in the US and in other countries, in approximately 15 clinical sites.

After informed consent is obtained, patients will enter a screening phase for no more than 3 days, to determine eligibility. Approximately 40 eligible patients will be randomized to receive either opaganib added to standard of care, or matching placebo added to standard of care, in a randomization ratio of 1:1. Treatment assignments will remain blinded to the patient, investigator and hospital staff, as well as the sponsor. As there is currently no consensus for a definitive treatment specifically targeting the SARS-CoV-2 virus causing COVID-19 (K. Wilson, 2020), standard of care will refer to regional, institutional or physician directed therapies, that may be implemented during the COVID-19 pandemic.

Study participants will receive either opaganib 2 x 250 mg capsules (500 mg) every 12 hours, or matching placebo, in addition to standard of care (pharmacological and/or supportive). Study drug will be administered every day for 14 days (Day 1 to Day 14), unless the patient has been discharged from the hospital without requiring supplemental oxygen, in which case study drug will only be administered to Day 10.

All participants will be followed up for 4 weeks after their last dose of study drug, which may occur at the end of the 2-week double-blind treatment phase or after premature study drug discontinuation, based upon patient or physician determination.

The maximum duration of study participation will be 45 days (including up to 3 days screening; 2 weeks double-blind (DB) phase and 4-weeks off-study drug follow-up).

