# 5.2 Specification of Baseline Values

In general, Baseline will be defined for each subject as the last available, valid, nonmissing assessment before first study drug dose.

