### 8.4 Clinical Laboratory Tests

Laboratory assessments, providing indication of safety, include serum chemistry (Glucose, Blood Urea Nitrogen, Sodium, Chloride, Creatinine, Potassium, Calcium, Uric Acid, Total Protein, Albumin, Total Bilirubin, Alkaline Phosphatase, Aspartate Aminotransferase, Alanine Aminotransferase, Bicarbonate) and hematology (Red blood cell count, Hemoglobin, Hematocrit, Platelets, White blood cell count, Neutrophils, Lymphocytes, Monocytes, Eosinophils, Basophils), and will be collected during Screening visit and then once weekly at Day 7 and Day 14 visits. Urinalysis is scheduled to be collected only in Screening visit.

Laboratory results will be assessed versus normal ranges (provided locally for each site) and abnormal results will be further classified as clinically significant (Yes/No). In addition, results will be graded using the NCI CTCAE v5.0 criteria.

Chemistry and Hematology laboratory tests will be presented at baseline, Day 7 and Day 14 visits. Laboratory tests results and changes from baseline to each visit will be summarized using descriptive statistics for continuous variables.

The incidence of abnormal results and of clinically significant abnormal results will be summarized for laboratory data using frequencies and percentages, per analyte and timepoint, including 'any time post-baseline' time point.

Shifts (below, within, and above the normal range) from baseline to each visit and 'any time post-baseline' will be summarized using patient counts. Similarly, shifts in interpreted result (normal, abnormal high clinically significant result, and abnormal low clinically significant) will be provided. In shift analysis to any time during study, the worst outcome in both directions (Low, High) will be considered (A subject may be counted both as a shift to High and as a shift to Low, if experienced both events during the study).

In addition, laboratory tests will be summarized by maximal toxicity grade.

Denominators for percentages will equal the number of subjects in the safety population providing data for specific time point.

Listings for clinically significant abnormal laboratory data will be presented.

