## 8.7 Electrocardiography

12-lead electrocardiogram will be performed for all subjects during screening visit and at Day 14 visit. For patients on concomitant hydroxychloroquine, the 12-lead ECG will be repeated after 3 hours ( $\pm 30$ mins) of initial dose, on Day 2 and Day 4.

Incidence of abnormal result and of abnormal clinically significant results will be summarized using appropriate descriptive statistics. Summaries may be provided separately for the subjects on concomitant hydroxychloroquine.

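### Protocol 12.1.2 allows screening from Day -7 while every other statement allows 3 days, so eligibility chemistry, blood counts and ECG could be 7 days old at first dose

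*Protocol*

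**What the plan says.** The sentence in Protocol 12.1.2 reads "Screening may be performed prior to Baseline (Day -7 to -1", and it also allows screening on Day 1 itself. The heading of that section gives Day -3 to Day 1.

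The other statements of the window agree with the heading:

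- Protocol 10.1: "patients will enter a screening phase for no more than 3 days, to determine eligibility". The synopsis and SAP 3.1 say the same.
- Protocol synopsis, Study Duration: "maximum duration of study participation will be up to 45 days (including up to 3 days screening". Protocol 10.1 and SAP 3.1 repeat the 45-day total.
- The screening column in Protocol Section 4 (Table 1) and in SAP Table 1 runs from Day -3 to Day 1.

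On the timing of the tests, SAP 8.4 says that chemistry and hematology "will be collected during Screening visit and then once weekly at Day 7 and Day 14 visits", and SAP 8.7 says "12-lead electrocardiogram will be performed for all subjects during screening visit and at Day 14 visit". SAP 5.2 defines baseline in general as the "last available, valid, nonmissing assessment before first study drug dose", without a limit on its age.

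**The concern.** Screening results decide who may be dosed. Exclusion 9 is an example: "Corrected QT (QTc) interval on electrocardiogram (ECG) >470 ms for females or >450 ms for males". Exclusions 10 to 15 cover liver enzymes, bilirubin, creatinine, neutrophils, platelets and hemoglobin.

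The patients are hospitalised, need oxygen, and have a disease that Protocol 6.1 says can progress to ARDS with multiorgan failure. In such patients a creatinine, platelet count or QTcF from a week earlier may no longer describe the person about to receive the drug. Only the pregnancy test has its own 3-day limit. For every other eligibility test the screening window is the only limit on age, and this sentence widens it.

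There is a smaller analytic consequence. If no later pre-dose value is recorded, the old result also serves as baseline for the laboratory summaries (SAP 8.4) and the exploratory inflammation markers (SAP 7.4). That would add noise and could shift the within-arm change from baseline.

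**Working it through.** **1. Which window is intended.** The inputs are the treatment phase of 2 weeks (14 days), the follow-up of 4 weeks (28 days) and the stated maximum participation of 45 days (synopsis, Protocol 10.1, SAP 3.1).

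Maximum participation = screening + treatment + follow-up.

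- 3-day screening: 3 + 14 + 28 = 45 days, which reproduces the stated figure.
- Day -7 screening: 7 + 14 + 28 = 49 days, which is 49 - 45 = 4 days over it.

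So 3 days is the intended window and the sentence in 12.1.2 is the outlier. Two other places in the protocol also carry times that do not fit a 14-day treatment: the safety objective in 7.4 refers to 4 weeks of dosing, and 12.1.4 allows an end-of-treatment ECG at Day 28. That pattern is consistent with a remnant.

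**2. Age of a screening test at first dose.** First dose is on Day 1. Protocol 12.1.2 goes from Day -1 straight to Day 1, so there is no Day 0, and a test on Day d (d negative) has age (1 - d) - 1 = -d.

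| Earliest screening day | Age at first dose, no Day 0 | Age if a Day 0 were counted |
|---|---|---|
| Day -3 | 3 days | 4 days |
| Day -7 | 7 days | 8 days |

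The gap is 4 days under either convention.

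**3. Whether a later scheduled test replaces the screening result before dosing.** From the Section 4 schedule, Protocol 12.1.4, and SAP 7.4, 8.4 and 8.7:

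| Assessment | Next scheduled after screening | Scheduled pre-dose repeat? |
|---|---|---|
| Chemistry, CBC | Day 7 | No |
| Inflammation markers | Day 7 | No |
| ECG | Day 14; for hydroxychloroquine users about 3 hours after the first dose, then Days 2 and 4 | No |
| Oxygen flow, vital signs | Day 1 | Scheduled again on Day 1 |
| Pregnancy test | None | Not needed: has its own 3-day limit |

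**4. How many criteria depend on these tests.** In Protocol 9.2 these are no. 9 (QTcF), 10 (AST/ALT), 11 (bilirubin), 12 (creatinine), 13 (neutrophils), 14 (platelets) and 15 (hemoglobin): 7 of 20.

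**5. What is not affected.** Oxygen flow is scheduled again on Day 1, so the primary AUC baseline does not depend on the screening window. Screening precedes allocation, so older values can occur in both arms alike. They do not bias the between-arm comparison.

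**The case against.** The strongest counter-argument is that this is an isolated slip with little practical reach.

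- Protocol 12.1.1 sends the reader to Section 4 for the detailed schedule, and the 3-day limit in 10.1 is a firm cap. A site would have to disregard both, and the section's own heading, to screen on Day -7.
- Patients must be in hospital during screening and at baseline. Footnote 5 of the schedule leaves laboratory draws to the investigator according to clinical condition, and exclusion 1 allows the investigator to keep out anyone with a co-morbidity that adds risk. A deteriorating patient could therefore be retested or excluded.
- Weekly chemistry and CBC are accepted during dosing.
- SAP 5.2 takes the last available pre-dose value, so any later recorded result displaces the screening value.
- The count of 7 criteria says nothing about how many patients would be misclassified, and no document shows that anyone was screened before Day -3.

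Much of this stands as a limit on the size of the problem. The exposure is conditional: it needs a site to follow the sentence and no retest to be done. The number of patients affected is unknown, and 49 against 45 days is evidence of the contradiction, not a second harm.

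It does not remove the point. Each safeguard is optional, and none requires a result within 3 days of first dose. No clause makes Section 4 override 12.1.2, so a site using Day -7 could cite explicit permission. The SAP's precedence rule (Preface) does not help, because sites screen from the protocol. Weekly monitoring during treatment serves a different purpose from establishing eligibility.

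**Conclusion.** The point holds. Protocol 12.1.2 contradicts its own heading and every other statement of the screening window, and the 45-day total confirms that 3 days is meant. As written, the sentence permits chemistry, CBC and ECG results 7 days old at first dose instead of 3, and 7 of the 20 exclusion criteria depend on them.

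This assumes day numbering without a Day 0, a site that follows the body text, and no unscheduled pre-dose repeat. The consequence is for eligibility and patient safety, with a minor effect on laboratory and inflammation-marker baselines. The primary AUC baseline, the vital-sign baseline, the pregnancy criterion and the randomised comparison are unaffected. It should be corrected, but it does not threaten the primary result.

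**What to change.** In Protocol 12.1.2, change the pre-baseline window from Day -7 to -1 to Day -3 to -1. The 3-day limit then applies to all eligibility laboratory tests and the ECG, and the section agrees with its heading, the synopsis, Section 4, Protocol 10.1, SAP 3.1 and the 45-day maximum. No other text has to change for this point.

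The cost is one line in an amendment, with no effect on sample size, visits or analysis.
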